12.1.2 Coding of Adverse Events

Adverse events will be coded using MedDRA, Version 23.0 or later.

12.1.3 Classification of Adverse Events

Adverse events will be classified according to the time of onset of the adverse event:

- *pre-treatment adverse event* – an adverse event that starts on or after the date the patient signed the *Informed Consent Form* and prior to the date of first dose of IMP. As such, this definition will only be used for *de novo* patients.
- *treatment-emergent adverse event (TEAE)* – *an adverse event that starts or increases in intensity and/or seriousness on or after the date of first dose of IMP*

Adverse events, sorted by system organ class (SOC) and preferred term, will be summarized by treatment group.

An adverse event is considered causally related to the use of the IMP when the causality assessment by the investigator is *probable* or *possible*. For pre-treatment adverse events, a causality assessment is not relevant.

12.1.4 Allocation of TEAEs to Treatment Periods

TEAEs will be allocated to treatment periods according to the time of onset of the adverse event:

Pre-treatment AEs – an adverse event that starts on or after the date the patient signed the Informed Consent Form and prior to the date of first dose of IMP in Open Label Period. This definition will only be used for *de novo* patients.

TEAE in the Open Label Period – an AE that starts on or after the date of the first IMP intake in the Open Label Period and before the date of the end of Open Label Period. In addition, for *de novo* patients only, this also includes AEs that start before the date of the start of Open Label Period and worsens before the date of the end of the Open Label Period.

TEAE in the Double-Blind Treatment Period – a TEAE that starts on or after the date of the first IMP intake in the Double-Blind Treatment Period and before the date of the end of Double-Blind Treatment Period, **OR** starts before the date of the start of Double-Blind Treatment Period and worsens on or after the date of the first IMP intake in the DB treatment period and before the date of the end of the Double-Blind Treatment Period

TEAE in the Safety Follow-up Period – an AE that starts on or after the date of the end of Double-Blind Treatment Period or on or after the date of withdrawal (in either the Open Label Period or the Double-Blind Treatment Period).

Adverse events that are ongoing in either parent study at the time of entry into the current study will be included in the present study. All data will be transcribed and the rules as described above will apply.

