8.2 Screening Visit (Visit 1)

The Screening visit will be performed only for *de novo* patients. Patients rolling over from Study 12709A will proceed directly to the Baseline Visit.

The screening period begins when the first screening assessment is done, after written Informed Assent/Consent has been obtained. If there is a need for washout of disallowed medication, it should be completed before any Baseline (Visit 2) assessment is done and must comply with the required washout periods in [Appendix II](#).

The Baseline visit should be scheduled 5 to 15 days after the Screening Visit. However, in exceptional cases, the visit interval between the Screening and Baseline Visits may be extended up to 30 days with consent from the Medical Monitor, provided the Medical Monitor accepts the rationale provided for the extension.

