16.8.9 Analysis of Adverse Events

Adverse events will be classified according to the time of onset of the adverse event:

- *pre-treatment adverse event* – an adverse event that starts on or after the date the patient signed the *Informed Consent Form* and prior to the date of first dose of IMP
- *treatment-emergent adverse event* (TEAE) – an adverse event that starts or increases in intensity on or after the date of first dose of IMP

Adverse events, sorted by system organ class (SOC) and preferred term, will be summarized by treatment group.

Allocation of TEAEs to Study Periods

TEAEs may be allocated to study periods (these will be defined in the *Statistical Analysis Plan*).

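### SAP 12.1.4 sets no earliest date for worsening in the open-label TEAE rule, so read literally it can flag an event that began and worsened before the first dose, contrary to SAP 12.1.3

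*SAP*

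**What the plan says.** SAP 12.1.3 defines a TEAE as "an adverse event that starts or increases in intensity and/or seriousness on or after the date of first dose of IMP". Protocol 16.8.9 has the same date condition, on intensity only: "an adverse event that starts or increases in intensity on or after the date of first dose of IMP".

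SAP 12.1.4 then assigns events to periods. Its lead-in reads "TEAEs will be allocated to treatment periods according to the time of onset of the adverse event". The list that follows has four items.

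- **Pre-treatment AEs** (de novo patients only) are set by start date alone: on or after consent and before the first open-label dose.
- **Open-label TEAEs** are AEs that start from the first open-label intake and before the end of the period. For de novo patients, "this also includes AEs that start before the date of the start of Open Label Period and worsens before the date of the end", meaning when the open-label period closes.
- **Double-blind TEAEs** have a parallel worsening limb for events that started earlier. It applies where the event "worsens on or after the date of the first IMP intake in the DB treatment period and before the date of the end" of that period.
- **Safety follow-up TEAEs** are set by start date.

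**The concern.** The open-label and double-blind worsening limbs do the same job, but only the double-blind limb says that the worsening must follow the first intake in its period. The difference looks like a drafting omission. It leaves SAP 12.1.4 wider than the definition that it is meant to apply.

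The affected type of event can arise in this trial. Protocol 10.1.1 has AEs recorded from consent, and protocol 10.3 has changes in intensity logged. Protocol 8.2 states: "The Baseline visit should be scheduled 5 to 15 days after the Screening Visit". The same section allows up to 30 days in exceptional cases, and washout of disallowed medication may fall in this interval.

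At stake is the TEAE flag. It feeds the overview and listings (SAP 12.1.5), the open-label TEAE summaries (12.1.7), and the summaries of treatment-emergent SAEs and of TEAEs leading to withdrawal (12.1.9 and 12.1.10). The open-label period has no control group. A wholly pre-dose event shown there as treatment-emergent would therefore have no comparator beside it.

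**Working it through.** The plan gives no figure to reproduce here, because the question is one of date logic. I wrote the rules as conditions and applied them to example events in a de novo patient.

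**Inputs.** S = start day, W = worsening day, D = day of first open-label dose, B = start of the Open Label Period, E = its end. Illustrative values (assumed): consent on day −10, B = 0, E = 84 (12 weeks × 7 days), and D = 0 or 1.

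**Rules**

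- Pre-treatment (12.1.4): −10 ≤ S < D
- TEAE (12.1.3): S ≥ D, or W ≥ D
- Open-label TEAE as written (12.1.4): D ≤ S < E, or (S < B and W < E)
- Open-label TEAE with the wording recommended under the fix: D ≤ S < E, or (S < D and D ≤ W < E)

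**Key case: S = −8, W = −3, D = 0**

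- Pre-treatment: −10 ≤ −8 < 0, so yes.
- 12.1.3: −8 ≥ 0 is false and −3 ≥ 0 is false, so not a TEAE.
- 12.1.4 as written: −8 < 0 and −3 < 84, so an open-label TEAE.
- Recommended wording: 0 ≤ −3 is false, so not an open-label TEAE.

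**All cases**

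| S | W | D | Pre-treatment | TEAE by 12.1.3 | Open-label TEAE as written | Recommended wording |
|---|---|---|---|---|---|---|
| −8 | none | 0 or 1 | yes | no | no | no |
| −8 | −3 | 0 or 1 | yes | **no** | **yes** | no |
| −8 | day D | 0 or 1 | yes | yes | yes | yes |
| −8 | 20 | 0 or 1 | yes | yes | yes | yes |
| 0 | 20 | 0 | no | yes | yes | yes |
| 0 | 20 | 1 | yes | **yes** | **no** | yes |
| 5 | none or 20 | 0 or 1 | no | yes | yes | yes |

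The two sections disagree in two rows. The second row is the subject of this point. If 12.1.4 is read as applying only to events that are already TEAEs under 12.1.3, that row becomes no, and the conflict disappears.

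The sixth row is a smaller mismatch in the other direction. It arises only if the first dose is taken after the day on which the period starts, because the limb counts from the start of the period and not from the first intake.

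Adding only a lower bound on the worsening corrects the second row and changes nothing else. Counting the start from the first intake as well corrects the sixth. The last column then agrees with 12.1.3 in every row.

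**Cross-check against SAP 16.2.4.** An AE with no start date that stopped before the first dose is classed as pre-treatment. An AE with complete dates that started, worsened and stopped in screening meets the open-label limb as written. On the literal reading, the better-documented event gets the less accurate class.

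**The case against.** The strongest reply is that the SAP classifies first and allocates second. Section 12.1.3 decides what a TEAE is. The title and lead-in of 12.1.4 refer to allocating TEAEs, and protocol 16.8.9 leaves to the SAP only the definition of study periods for that allocation. On this reading a wholly pre-dose event fails the first step and is never allocated.

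This is plausible, and it is why the documents do not support a stronger statement that such events will be counted as TEAEs. It is not decisive. The 12.1.4 list itself contains pre-treatment AEs, so it is not confined to TEAEs. Its open-label item also speaks of AEs where the double-blind item speaks of a TEAE.

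A reader might infer two further harms, and neither follows.

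- **Double counting.** An AE that starts before dosing and worsens after it is both pre-treatment and an open-label TEAE under every reading (third and fourth rows). SAP 16.3.2 also allows an event to sit in more than one period when its intensity increases or it becomes serious. Overlap is therefore not a consequence of the missing bound alone.
- **Attribution to vortioxetine.** Causally related TEAEs are tabulated separately, on the investigator's assessment, and SAP 12.1.3 treats causality as not relevant for pre-treatment events. The listings in 12.1.1 give start date, days since first dose and each intensity, so a misplaced event would be visible.

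One further objection stands. The limb is limited to de novo patients, so a better date bound does not by itself bring 12709A rollover patients into line with 12.1.3.

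**Conclusion.** The open-label worsening limb in SAP 12.1.4 lacks an earliest date for the worsening. It conflicts with SAP 12.1.3, protocol 16.8.9 and its own double-blind counterpart. On the literal reading, an AE that started and worsened before the first dose can carry an open-label TEAE flag that 12.1.3 would deny it.

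The reach is narrow. The AE must belong to a de novo patient, and must both start and worsen between consent and the first dose. It can enter only the descriptive open-label tables, in the de novo column and the overall column that includes it. The primary endpoint is unaffected. So is the randomized TEAE comparison, because the double-blind limb has the bound.

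A reader might want a size in percentage points. The documents do not support one: they give about 150 enrolled patients without splitting de novo from 12709A rollover, and no rate of AEs in screening. The effect is probably small and could be zero. This is a low-severity wording correction.

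**What to change.** Reword the open-label worsening limb to cover *a TEAE that starts before the first IMP intake in the Open Label Period and worsens (in intensity and/or seriousness) on or after that intake date and before the Open Label Period ends*.

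This makes three changes:

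- It adds the missing lower bound, as in the double-blind limb.
- It counts the start from the first intake and not from the start of the period.
- It says TEAE and names seriousness, so that 12.1.3 governs.

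The double-blind limb could carry the same parenthesis for consistency.

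The cost is one phrase in the SAP and the matching line in the programming specification. No new data or analysis is needed.

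The rewording leaves the restriction to de novo patients as it is. Whether an ongoing AE in a 12709A rollover patient that worsens in the open-label period should also be captured is a separate question, which the sponsor should answer in the same edit.

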8.5 Withdrawal Visit

Open-label Period: Patients who withdraw from the study prior to Visit 8 will be asked to attend a Withdrawal Visit, if at all possible. The visit must be scheduled as soon as possible after withdrawal. Patients who withdraw from treatment will also be asked to attend a Safety Follow-up Visit.

Patients who do not fulfil randomization criteria for remission or adequate response at Week 10 and/or Week 12 will be withdrawn from the study and will complete an early Withdrawal Visit.

Double-blind Period: Patients who withdraw from the study prior to the Completion Visit after 26 weeks of treatment in the double-blind period will be asked to attend a Withdrawal Visit, if at all possible. The visit must be scheduled as soon as possible after withdrawal. Patients who withdraw from the study will also be asked to attend a Withdrawal Visit (Visit 17, where both efficacy and safety are assessed).

No new information will be collected from patients who withdraw from the study, except information collected in relation to the scheduled Withdrawal Visit or needed for the follow-up of adverse events (section 10.5).

The reason for withdrawal must be recorded in the eCRF.

For a patient and/or the patient's parent(s)/legal representative(s) who withdraw consent:

- if the patient and/or the patient's parent(s)/legal representative(s) withdraw consent during a visit and then agree(s) to it being the final visit, the investigator will complete the visit as a Withdrawal Visit and all the data collected up to and including that visit will be used
- if the patient and/or the patient's parent(s)/legal representative(s) withdraw(s) consent during a telephone conversation, the investigator will ask the patient if he or she will attend a Withdrawal Visit. If the patient:
 - agrees to attend a Withdrawal Visit, all the data collected up to and including that visit will be used
 - refuses to attend a Withdrawal Visit, the investigator should attempt to follow the patient's safety and future treatment; any information collected will only be recorded in the patient's medical records
- if the patient and/or the patient's patients/legal representative explicitly request(s) that the patient's data collected from the time of withdrawal of consent onwards not be used, this will be respected

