4.2 Definition of Periods

The following periods can be identified:

Screening period

A Screening Visit will be performed only for de novo patients. Patients rolling over from Study 12709A will proceed directly to the Baseline Visit. Therefore, the screening period is not applicable for these patients. In addition, this period is not applicable for patients rolling over from Study 12712A, as these patients will enrol the study at the randomization visit. The screening period begins when the first screening assessment is done after written Informed Assent/Consent has been obtained, and ends at the Baseline Visit for the Open Label Period (visit 2).

Open Label Period

De novo patients who continue to meet all inclusion criteria and none of the exclusion criteria (see section 5.3 of the study protocol) will be enrolled into a 12-week Open Label Period. For patients rolling over from Study 12709A, the Baseline Visit of the Open Label Period will be performed the same day as the Week 12 (Completion) Visit of Study 12709A.

Patients eligible for entering the Open Label Period will start IMP (vortioxetine) at the Baseline Visit of the Open Label Period.

The duration of the Open Label Period is 12 weeks or until the patient is withdrawn from the study, whichever comes first. If a patient withdraws from the study, the Open Label Period ends at the withdrawal visit.

Double-Blind Treatment Period

The Double-Blind Treatment Period starts at the randomization visit (visit 8) and ends after 26 weeks of treatment (visit 17), or until the patient will be withdrawn from the study, whichever comes first. If a patient withdraws from the study the Double-Blind Treatment Period ends at the withdrawal visit.

Patients rolling over from Study 12712A will have their first visit in this study at visit 8 (the Randomization Visit). For 12712A-patients the last available values from assessments and procedures (efficacy/safety, and use of concomitant medication) performed at either Visit 7 (Week 8) and/or Visit 8 (Week 10), or Visit 9 (Week 12) in Study 12712A will be the Randomization Visit values for this study.

Safety Follow-up Period

The Safety Follow-up Period has a duration of 4 weeks after the last IMP intake. This period starts at the date of last IMP intake.

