A Safety Follow-up Period is planned at the end of the study (i.e. after completion of visit 17) and after withdrawal of a patient in either the Open Label Period or the Double-Blind Treatment Period. The end of the Safety Follow-up Period will be at visit 18 (SFU visit).

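### SAP 12.1.4 leaves end-day AEs, and worsening of AEs carried over from Study 12709A, out of the period TEAE tables, and SAP 12 uses the APRS where the protocol says FAS (minor)

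*SAP*

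**What the plan says.** **Period windows.** SAP 12.1.4 places TEAEs by onset date. The double-blind window opens on the day of the first double-blind dose and admits only events that start "before the date of the end of Double-Blind Treatment Period". The open-label window has the same open upper end. Safety Follow-up receives "an AE that starts on or after the date of the end of Double-Blind Treatment Period or on or after the date of withdrawal", for withdrawals in either period.

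**Period limits.** SAP 4.2 ends double-blind for a completer at Visit 17. For a withdrawn patient, "If a patient withdraws from the study the Double-Blind Treatment Period ends at the withdrawal visit". For open label, "The duration of the Open Label Period is 12 weeks or until the patient is withdrawn from the study, whichever comes first", and the next sentence puts the end for a withdrawn patient at the withdrawal visit. On Safety Follow-up, 4.2 says "The Safety Follow-up Period has a duration of 4 weeks after the last IMP intake" and "This period starts at the date of last IMP intake", but also "The end of the Safety Follow-up Period will be at visit 18". Protocol 8.5 says of the withdrawal visit: "The visit must be scheduled as soon as possible after withdrawal". The withdrawal date and the visit date can therefore differ, although footnote d of protocol Panel 2 lets an open-label visit be converted to a withdrawal visit on the same day.

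**Worsening.** SAP 12.1.3 and protocol 16.8.9 define a TEAE by onset or increase in intensity from the first dose onwards (the SAP adds seriousness), with no limit by inclusion source. For open label, SAP 12.1.4 counts worsening of an AE that began earlier for de novo patients only. The same section brings AEs still ongoing in a parent study into this study under the same rules.

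**Analysis set.** Protocol 16.8.8 bases safety on the APES and the FAS. SAP 12 uses the APES for open label and the APRS for double-blind. SAP 5 names the APRS for safety only for 12712A rollovers. The FAS requires a dose of double-blind IMP and the APRS does not. Protocol 5.5 foresees patients randomized in error who have taken no IMP.

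**The concern.** A period TEAE table should count every event that arose or worsened on that period's treatment, among the patients who received it. Three written rules depart from this.

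- The last day of the period is excluded. SAP 12.1.7 plans TEAE tables for open label and double-blind only, so end-day events have no TEAE table there. In protocol Panel 3, Visit 17 (completion or withdrawal) is one of two visits after randomization with laboratory tests, ECG, weight and examinations, and clinically significant findings must be recorded as AEs. Relapsers must also be withdrawn, so withdrawal visits will be common.
- An AE carried over from Study 12709A that worsens on open-label vortioxetine is a TEAE by definition but is not allocated to open label.
- An undosed randomized patient enters the double-blind denominator.

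SAP 4.2 and 12.1.4 also start Safety Follow-up on different dates, so two programmers could place the same event in different periods. At stake is the accuracy and reproducibility of descriptive safety tables in a paediatric trial with 40 patients per arm.

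**Working it through.** The documents state no TEAE incidence and no count of affected patients, so there is no figure of the plan's own to reproduce.

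**Step 1: apply the date rules of SAP 12.1.4.** SAP Panel 6 gives Visit 8 = day 84 and Visit 17 = day 266. Open label requires first open-label dose ≤ onset < open-label end. Double-blind requires first double-blind dose ≤ onset < double-blind end. Follow-up requires onset ≥ double-blind end or onset ≥ withdrawal date. Visit 8 is taken as the end of open label, as Panel 6 labels it.

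| Case | Open label | Double-blind | Follow-up |
|---|---|---|---|
| Completer, onset day 266 | no | no (266 is not < 266) | yes |
| Withdrawn at Visit 8, onset day 84 | no (84 is not < 84) | not entered | yes |
| Onset day 84, first double-blind dose day 84 | no | yes | no |
| Onset day 84, first double-blind dose day 85 | no | no | no |
| Withdrawn day 200, withdrawal visit day 205, onset day 202 (assumed days) | no | yes (202 < 205) | yes (202 ≥ 200) |

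The first two events leave the period tables. The third moves to the double-blind table and is not lost. The fourth has no period. The fifth has two. If the withdrawal visit takes place on the withdrawal day, the fifth case does not arise.

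**Step 2: size of the end-day rule.** The arm size is 40 (protocol 16.10). If 0, 1 or 2 patients (assumed) have their only qualifying event on the end day, incidence falls by 0/40 = 0, 1/40 = 2.5 or 2/40 = 5.0 points. If the patient has another qualifying event in the period, only event and preferred-term counts change.

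As a rough expectation, assume onsets uniform over 26 × 7 = 182 days and 20 of 40 patients with one event each. The end day holds 1/182 = 0.55% of onsets. That gives 20 × 1/182 = 0.11 patients, or 0.11/40 = 0.3 points. For a patient withdrawn at Week 4 the share is 1/28 = 3.6%. If sites date visit findings to the visit day, the uniform assumption understates the effect; the documents do not settle this.

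**Step 3: size of the worsening rule.** With about 150 patients enrolled (protocol 5.1), one 12709A rollover whose only open-label TEAE is a worsening changes the open-label total by about 1/150 = 0.7 points.

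**Step 4: size of the APRS denominator.** Assume one undosed patient among 40 randomized to an arm.

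- 4 patients with a TEAE: 4/40 = 10.0% against 4/39 = 10.3%.
- 20 patients with a TEAE: 20/40 = 50.0% against 20/39 = 51.3%.
- No undosed patient: no change.

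**The case against.** The strongest reply is that this is housekeeping. Every AE stays in the listings with a TEAE flag (SAP 12.1.5), C-SSRS results are summarized separately (12.5.1), the expected end-day loss is 0.3 points on the assumptions above, and the number affected may be zero. That stands, and it sets the priority. It does not remove the contradictions, which are in written rules and not in missing detail.

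A reader might also infer more than the documents support.

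- *Each rule lowers TEAE incidence whenever any patient is affected.* It does not. Patient-level incidence falls only if the event is that patient's only qualifying event in the period, and a Visit 8 event with a same-day double-blind dose only changes table. Excluding that day from open label then prevents double counting.
- *The open-label worsening rule admits worsening before the first dose, because it lacks the lower date bound of the double-blind rule.* SAP 12.1.4 opens by allocating TEAEs, and 12.1.3 already requires onset or worsening from the first dose onwards. The bound is implied, though the wording could be tidier.
- *SAP 16.3.2 also contradicts the de novo restriction.* That section concerns events assigned to more than one period, and Study 12709A is not a period of this study. The clear conflict is with 12.1.3 and protocol 16.8.9.
- *End-day events vanish from every summary.* This is certain only for the 12.1.7 tables. The term treatment period in 12.1.9 and 12.1.10 is not defined and could be read to include follow-up.
- *An undosed patient can never have a double-blind TEAE.* This is nearly right, but SAP 16.2.1 imputes a missing IMP start date for 12712A rollovers. Read literally, that could give an undosed rollover a start date.

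Finally, protocol 16.8.9 leaves period allocation to the SAP, so the boundary problem is internal to the SAP. The analysis set and the worsening rule depart from the protocol.

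**Conclusion.** The point holds in three limited parts. (a) AEs starting on the Visit 17 or withdrawal day are left out of the 12.1.7 TEAE tables, a Visit 8 AE is lost only if the first double-blind dose comes later, and Safety Follow-up has two start dates. (b) Worsening on open-label vortioxetine of an AE carried over from Study 12709A is left out of the open-label TEAE tables, against the TEAE definition. (c) The double-blind safety set differs between protocol 16.8.8, SAP 12 and SAP 5, and an undosed randomized patient would dilute TEAE percentages.

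The sizes, 2.5 points for each patient in an arm of 40 whose only qualifying event falls on the end day and 1.3 points for one undosed patient at about 50% incidence, rest on assumed counts. A reader might infer that the rules favour one arm or touch the primary result. The documents do not support that: the same rules apply to both arms, no count by arm is given, and the efficacy analyses use relapse dates and the FAS. The priority is minor.

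**What to change.** - **SAP 4.2 and 12.1.4, boundary.** Define one period-end date, count AEs starting on or before it in that period, and start Safety Follow-up the next day. The Visit 17 or withdrawal-visit date fits 4.2 best, though other conventions are defensible. State which date applies when no withdrawal visit is attended, since 16.2.2 does not impute a missing withdrawal date. Align the last-intake start and the 4-week duration in 4.2 with this boundary.
- **Open label to double-blind.** For patients entering from open label, split at the first double-blind dose date: earlier onsets to open label, onsets on or after it to double-blind. For 12712A rollovers, who have no open-label period here, list AEs between randomization and first double-blind dose separately as pre-dose.
- **SAP 12.1.4, worsening.** Apply the open-label rule to all open-label patients, for worsening on or after the first open-label IMP intake. For de novo patients this only makes explicit what 12.1.3 implies. For 12709A rollovers it keeps out worsening that occurred in the parent study.
- **SAP 5 and 12, analysis set.** Base double-blind safety tables on the FAS as in protocol 16.8.8, make the two SAP sections agree, and list AEs in undosed randomized patients separately.

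The cost is SAP wording, a date comparison and an analysis-set flag in the programs. No new data are needed. Reported incidences may shift slightly.
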